5.3 Patient Recruitment

All eligible patients will be recruited to Step 1 by MATCH site research staff at the time that they enroll in the MATCH Master (Screening) Protocol or will be undergoing clinical tumor profiling at a select expansion site.

Potential participants at expansion sites will be approached by site research staff after permission of the treating physician.

At sites participating in the Substudy (Step 2), potential Substudy participants will be identified according to the selection criteria (see Section [3.2](#)). MATCH or other site research staff will notify potential participants, introduce the study and consent interested participants.

We will collaborate with the ECOG-ACRIN Underserved Populations Recruitment and Retention Subcommittee to develop recruitment strategies to facilitate the enrollment of a diverse sample of participants. [name] is chair of this subcommittee, and she is also involved in an initiative to facilitate minority accrual to the MATCH trial (“Impact”) and will contribute her expertise to facilitate diverse patient participation for the proposed COMET trial.

Rev. 2/17

5.4 PRO/QOL Data Collection Process

Patient completed outcomes:

Patients will be recruited at the time of registration into the COMET study. At the time of registration at the sites, the patient's contact information should be collected on the Patient Contact (PC) form by the site CRA for all participants who do not have email/internet access (Note: all RCT Step 1 participants are required to have email/internet and thus no PC should be collected for these individuals). The completed PC should then be fax it to the OEAU and stored in a secure locking file storage location. Participants with email/internet access will be asked to enter this information themselves directly into the OEAU servers when they activate their EASEE-PRO account. The contact information is stored in a Biostatistics Center (BC) database and **IS NOT** linked to the master ECOG-ACRIN database. The OEAU RA will not have access to the main ECOG-ACRIN database that contains screening results.

Administration of web-based questionnaires will be coordinated by the OEAU. Administration of the questionnaires will be triggered based on completion of study milestones.

Questionnaire completion

Patients on Step 1, and those with e-mail access on Step 2, will be prompted to complete web-based forms via an e-mail. These e-mails will include a link to the web site for questionnaire completion. Each participant will be required to log in with their unique user ID and password to complete the requested instruments. The web site will reference a study-specific e-mail address and a toll-free phone number that patients can use to reach the OEAU staff should they have questions or need assistance. All participant data will be stored on a secure server.

Because the timings of survey completion in relation to events lie in very narrow windows, patients who do not complete the web questionnaires within 3 working days of the initial request e-mail will receive additional e-mail reminders. These reminder e-mails, like the initial e-mail, will provide a link to the current surveys, ask the participant to confirm that they have been able to access the web site, and provide both the e-mail address and the toll free help number for support.

If patients still have not responded within 12 days of the original e-mail, the OEAU Research Associate may attempt to telephone the patient and administer the questionnaire over the telephone. If questionnaires are telephone-administered, they will be marked as such in the data base. All surveys, while desired within 3 days of the event, will remain available for participants until either the surveys are completed or they are off-study. Since the completion date is recorded for all surveys, the study team will be able to make relevant determinations for inclusion of this data in specific analyses. However, after telephone follow-up, no additional or extraordinary means will be employed to collect overdue/missing questionnaires.

Only participants on Step 2 without email access may complete paper survey. The timing of administration will be the same as the web-based surveys.

Participants unable to enter their survey responses may designate a “scribe” to relay their responses. Participants will be able to indicate whether the survey was filled in by the participant or the designated scribe.

5.5 Study Instruments

NOTE: All participants of the Genetic Counseling substudy will complete surveys as shown in the Study Schema. Surveys will evaluate the primary and secondary endpoints informed by our theoretical models grounded in the Self Regulation Theory of Health Behavior¹⁸ and Diffusion of Innovation Theory¹⁷.

The study instruments are as follows:

5.5.1 *Knowledge of Genetic Disease (T0-T3; T0SS-T3SS):*

This will be evaluated using an adapted version of the Cancer Genetics Knowledge Scale and clin seq knowledge scale¹⁹⁻²¹. Adaptations were made for Somatic Testing. This scale is composed of items evaluating the differences between somatic and germline testing (3 items); the limitations of somatic testing (7 items), the limitations of germline testing (3 items) and relationship between tumor testing and clinical trials (1 item).

5.5.2 *Knowledge of Germline (i.e. inherited) Genetic Disease (T0SS-T3SS):*
This will be evaluated using an 8-item scale adapted from the Cancer Genetics Knowledge scale (Cronbach's $\alpha=0.58-0.60$)²¹. This scale includes items evaluating mechanism of inheritance (3 item), meaning of positive (2 items) and negative results (3 items).

5.5.3 *Health Literacy (T0 and T0SS):*
Health literacy is assessed using a 3-item scale for identifying patients with inadequate or marginal health literacy⁴⁹.

5.5.4 *Promis (assessments of emotional distress anxiety/emotional distress depression) (T0-T3; T0SS-T3SS):*
Emotional distress anxiety and depression are each assessed with the 4-item short Patient Reported Outcomes Measurement Information System (PROMIS), a system of highly reliable, precise measures of patient-reported health status for physical, mental, and social well-being^{50, 51}.

5.5.5 *State Anxiety (T0-T3; T0SS-T3SS):*
Measured with the 20-item State Inventory of the State-Trait Anxiety Inventory (STAII). The state scale is a sensitive indicator of transient or situational changes in anxiety (see Project 3, Section B.3.d)²⁴⁻²⁷.

5.5.6 *Cancer Specific Distress (T0-T3; T0SS-T3SS):*
Measured using the Impact of Events Scale (IES)^{28,29}. The 14 item IES is comprised of the Intrusion subscale (7 items) and the Avoidance subscales (7 items), which can be summed for the Total scale. Although the IES was developed to assess stress reactions following non-cancer-related traumatic events, it has more recently been utilized to assess response to cancer-related stressors, such as being at hereditary risk for cancer, which have been conceptualized as a continuous, rather than event-specific stressor^{25,30,31}. Thus, the IES has been used in the context of learning of one's genetic status, to assess cancer-specific distress over time^{25,26,31-34}. The IES has been validated in individuals experiencing many different kinds of stressors^{28,29,35}. On the bases of our preliminary studies, we have chosen not to use one item that did not have good face validity in our population. Thus, our modified IES will include 14 items (7 Intrusion; 7 Avoidant).

5.5.7 *Uncertainty About Genetic Testing (T0-T3 for tumor; T0SS-T3SS for germline):*
Assessed using a 3-item scale adapted from the uncertainty subscale of the Multi-dimensional Impact of Cancer Risk Assessment Question (MICRA)³⁶. This subscale has had high internal consistency in our related research (Cronbach's $\alpha=0.88$)¹⁸. This instrument has been adapted to address both germline and tumor genetic testing.

5.5.8 *Perceived Utility of Genetic Testing (T0-T3 for tumor; T0SS-T3SS for germline):*
This novel construct was developed to evaluate patient perceptions of the utility of germline and tumor genetic information for various aspects of their life and the life of their family members. It is comprised of 10-items and has had high internal consistency in our related research (Cronbach's $\alpha=0.90$)¹⁸.

5.5.9 *Preferences for Germline (i.e. inherited) Risk Information and Delivery (T2 only):*
We will assess preferences for learning germline information querying patients about interest in germline information if additional testing was needed and in the hypothetical situation where germline information was available as part of somatic testing. We will also assess preferences for delivery of germline information assessing provider (e.g. with a genetic counselor, medical oncologist) and mode of delivery (e.g. phone, videoconference, web-based genetic portal). These will be novel items developed specifically for the purpose of this study.
The genetic counselor will make recommendations for testing and will work with the local oncologist to facilitate germline confirmation testing through a contract with a commercial lab (likely Ambry Genetics based on an existing relationships). The local oncologist will be the ordering doctor.
We will use the standardized remote counseling communication protocols utilized in related research (COGENT R01 CA160847:[name], RESPECT R01 CA190871:[name]) and adapted for this context. Communication to at risk-relatives will be included in the standardized counseling protocols, which will be developed and finalized during the development period.

5.5.10 *Satisfaction with Receipt of Tumor Genetic Test Results (T2 only)*
This is a 9-item satisfaction with communication scale that evaluates participants' perceptions of their tumor profile test experience and of their experience receiving their tumor profile test results, including cognitive, affective and time/attention items. These scales were adapted for somatic testing^{52, 53, 54}.

5.5.11 *Preferences for Receipt of Tumor Genetic Test Results (T2 only)*
We will assess patient preferences for receipt of tumor profile test results, including queries related to the actual modes of sharing and receiving results, satisfaction with receiving results using these communication modes, and alternatives thereto. These will be novel items developed specifically for the purpose of this study.

5.5.12 *Satisfaction with Genetic Counseling Services (T1SS and T2SS only):*
Assessed with a 9-item satisfaction with communication scale items^{27,36,37} utilized in our prior and related studies and has demonstrated high internal consistency (Cronbach's $\alpha= 0.73-80$)^{15,16}.

5.5.13 *Regret and Disappointment Regarding Genetic Test Result (T2 and T3 for tumor; T2SS and T3SS for germline):*

Assessed with the 7-item Regret and Disappointment Scale (RDS) which has been utilized in the general population to assess regret and disappointment in decision making⁴⁸. This instrument has been adapted to address both germline and tumor genetic testing.

5.5.14 *Communication about Germline (i.e. inherited) Genetic Test Results (T2SS, T3SS)*

Psychosocial intention (T2SS) will be assessed using a 4-item measure of intent to communicate genetic test results previously developed and utilized in our COGENT study to assess intent to share genetic test results with health care providers, family members and other third parties.

Performance of psychosocial behaviors (T3SS) will be assessed using a 4-item measure of communication of genetic test results as described in the psychosocial intention.

5.6 Survey Assessment Schedule:

Please refer to Section [0](#) for Step 1 - Primary Study Intervention: RCT and Section [6.2](#) for Step 2 – Secondary Genetic Counseling Substudy.

5.7 Duration of Participation:

Patients can withdraw consent at any time. The duration of participation is anticipated to be no more than 4-5 months for those patients participating in the Primary Intervention Study. For those participating in the Substudy (Step 2), participation on this part is expected to be no more than 1 month if participants don't opt to have confirmatory germline genetic testing, or no more than 4 months if participants do have confirmatory germline genetic testing. For those participating in both the Primary Study (Step 1) and the Substudy (Step 2), participation is expected to last no more than 5 months.

Rev. Add5

5.8 Duration of Follow-up

For this protocol, all patients, including those who do not complete all steps, will be followed until the time of their last planned survey. Individual activity on the online genetic education web site will be followed through completion of all protocol therapy (if enrolled in MATCH).

In addition, all patients will be followed for survival per the standard ECOG-ACRIN follow-up schedule: at 3 months and 6 months after study entry.

Rev Add7 **6. Study Parameters**

Rev. 2/17

NOTE: All patients enrolled into Step 1 (including Arms A, B, and C) will be followed for survival per the standard ECOG-ACRIN follow-up schedule: at 3 months and 6 months after study entry.

Below is information specifically for patients enrolled into Arms A and B for the primary study.

Rev. 7/17
Rev Add7

6.1 Step 1 - Primary Study Intervention: RCT – Arms A & B

NOTE: Patients on Arm C (see Section [□□□□](#)) will not participate in or complete any primary study (Step 1) education or surveys, and will immediately be registered to Arm E and complete all of the substudy (Step 2) procedures.

Survey Schedule:

Surveys	Baseline	Post-Genetic Education (1-2 weeks after completion of T0)	Post-MATCH or Clinical Tumor Test Results Received ^A (within 3 days)	3 Months After the Receipt of MATCH or Clinical Tumor Test Results ^A
T0	X			
On-line Genetic Education (T1)		Arm A		
Usual Care/Standard Genetic Education (T1)		Arm B		
T2			X	
T3				X

^A. Refers to the written test report, not the notification of treatment assignment

Assessment Schedule:

Rev Add7

Primary Intervention Study (Step 1)						
Assessments ^A	T0	T1	T2	T3	3 Months	6 Months
Health Literacy	X					
Knowledge of Genetic Disease	X	X	X	X		
PROMIS Anxiety/Depression	X	X	X	X		
State Anxiety	X	X	X	X		
Cancer Specific Distress	X	X	X	X		
Uncertainty About Tumor Genetic Testing	X	X	X	X		
Perceived Utility of Tumor Genetic Testing	X	X	X	X		
Satisfaction with Receipt of Tumor Genetic Test Results			X			
Preferences for Receipt of Tumor Genetic Test Results			X			
Preferences for Germline (i.e. inherited) Risk Information and Delivery			X			
Regret and Disappointment Regarding Tumor Genetic Test Result			X	X		
Follow-Up ^B					X	X

^A. Descriptions of individual measures (except for Follow-Up) are included in Section [5.5](#). All instruments will be included as a single survey for each timepoint.

^B. All patients will be followed for survival per the standard ECOG-ACRIN follow-up schedule: at 3 months and 6 months after study entry.

6.2 Step 2 – Secondary Genetic Counseling Substudy – Arm D and Arm E

NOTE: The designated CRA must fax the MATCH or clinical tumor screening results report to the study team and discuss the results with the study team over telephone (See Section [4.2.3.3](#)).

Survey Schedule:

Survey	Baseline	Post-Remote Genetic Counseling ^A (within 3 days)	Post-Germline Testing Results Received ^B (within 3 days)	3 Months After Germline Testing Results Received ^B
T0SS ^C	X			
T1SS		X		
T2SS			X	
T3SS				X

A. Post-GC (Genetic Counseling) Visit 1, see schema for details

B. Post-GC (Genetic Counseling) Visit 2; see schema for details

C. For Arm D patients (i.e., from Step 1 Arm A or B patients), information taken from T2 (see Sec. 6.1) will be used to pre-populate T0SS, and only the remaining items in T0SS will need to be completed. The “Uncertainty” and “Perceived Utility of Genetic Testing” assessments in T2 are exceptions, and must be completed in T0SS for all patients. For Arm E patients (i.e. those from Step 1 Arm C), the entire T0SS will be completed as the baseline survey.

Assessment Schedule:

Secondary Genetic Counseling Substudy (Step 2)				
Assessment ^A	T0SS	T1SS	T2SS	T3SS
Health Literacy	X			
Knowledge of Genetic Disease	X	X	X	X
Knowledge of Inherited Genetic Disease	X	X	X	X
PROMIS Anxiety/Depression	X	X	X	X
State Anxiety	X	X	X	X
Cancer Specific Distress	X	X	X	X
Uncertainty About Germline (i.e. inherited) Genetic Testing	X	X	X	X
Perceived Utility of Germline (i.e. inherited) Genetic Testing	X	X	X	X
Satisfaction with Genetic Counseling Services		X	X	
Regret and Disappointment Regarding Germline (i.e. inherited) Genetic Test Result			X	X
Communication about Germline (i.e. Inherited) Genetic Test Results			X	X

A. Descriptions of individual measures are included in Section [5.5](#). All instruments will be included as a single survey for each timepoint.

Rev. 7/17 7. Statistical Considerations

Rev. Add6

The primary objective of the primary Intervention Study (RCT, Step 1) is to evaluate the efficacy of web-based pre-disclosure genetic education (i.e. before receipt of tumor profile results) on knowledge (genetic knowledge and knowledge of test benefits and limitations) and distress (anxiety, depression and cancer specific worry) compared to usual care services in patients undergoing tumor profiling for advanced cancer. The primary analysis will, thus, be based on patients who have survey data evaluable at both T0 (baseline) and T1 (post-genetic education) (or T2, post-disclosure of test results). Given the survey completion rate for both T0 and T1 is approximately 60% (as analyzed in May 2018), the accrual goal of the primary intervention study needs to be increased from 400 to 670 patients in order to maintain sufficient power for evaluating the effect of web-based pre-disclosure genetic education.

As MATCH has approached its goal of sequencing ~6000 patient tumors, this section incorporates changes to expand eligibility criteria (effective since Addendum #3) to allow patients from select sites who potentially undergo tumor profiling through non-MATCH assays and to increase the accrual goal (effective since Addendum #6). In this section, patients who enter COMET through MATCH Step 0 (prior to or after the activation of this addendum allowing for eligibility expansion) will be referred as the MATCH cohort, and other patients (who enter after the corresponding addendum activates) will be referred as the non-MATCH cohort.

7.1 Primary Study: Randomized Study of Web-based Pre-disclosure Genetic Education versus Usual Care (Step 1 – Arms A & B)

Rev. 2/17

NOTE: Patients on Arm C (see Section [□□□□](#)) will not participate in or complete any primary study (Step 1) education or surveys, and will immediately be registered to Arm E and complete all of the substudy (Step 2) procedures.

Rev. 7/17

7.1.1 *Primary endpoints* will include change in knowledge and distress (state anxiety, Promis anxiety, Promis depression and cancer specific distress) from baseline to post-education (T0 to T1) and baseline to post-disclosure (T0 to T2).

The following 10 analyses are of primary interest: change scores from T0 to T1, and T0 to T2 of each of the following five outcomes: knowledge, state anxiety, cancer specific distress, Promis anxiety and Promis depression, which correspond to 10 primary analyses. To account for the 10 primary analyses, A Bonferroni correction is considered here, setting the nominal p-value to declare statistical significance of $p < 0.005$ (5% Typical Type I error rate / 10 comparisons = 0.5% nominal p-value for declaring statistical significance). Preliminary data from the COMET pilot study (State Anxiety, IES-Total, Knowledge) is used to calculate power. As there was no preliminary data for Promis Depression/Anxiety in a similar setting, power calculation for these two measurements are based on data reported in Hinds et al. (2012). A sample size of 200 (with evaluable paired data) /arm is chosen here, which provides at least 85% power for all short-term outcomes (e.g. T0-T1) and changes in knowledge and cancer specific distress after receipt of tumor profiling results (e.g. T0-T2), using t test at two-sided 0.005 significance level.

With the completion rate for both T0 and T1 surveys at approximately 60% (as analyzed in May 2018) and the goal of evaluable sample size at 200/arm (at least for the analysis of changes between T0 and T1), the accrual goal of the primary intervention study needs to be inflated from 400 to 670 patients in order to maintain sufficient power for detecting proposed changes from T0 to T1 and changes in knowledge and cancer specific from T0 to T2 (as described in the preceding paragraph). With the completion rate for both T0 and T2 surveys at approximately 45% (as analyzed in May 2018), the projected evaluable sample size of 150 patients/arm can give the power of 72% for changes in knowledge and 95% for changes in cancer specific distress from T0 to T2. These 670 patients will be randomized 1:1 between the two arms, and the randomization will be stratified by gender, race, age (> 65 vs. ≤ 65), and education level. As of this analysis time, 320 patients have been enrolled into the primary intervention study. The current COMET accrual rate is approximately 15 patients per month (based on the last 3 months). Assuming 15, 20 or 25 patients per month (as more expansion sites are added over time) can be accrued to COMET from the select sites, it is expected to take 23, 17 or 14 additional months, respectively, to complete Step 1 accrual of 670 patients.

The original accrual plan posed a limitation on White patients at 80% of the accrual goal to ensure diversity of patients. Given that the accrual of this study might terminate early if the funding of this study ends, the accrual limitation on White patients is being lifted to ensure the maximal number of patients enrolled before funding ends.

Power for various sample sizes

Variable	Change score time period	Sample Size Per Arm	Power for p< 0.005, 2-sided	Change Score Group 1	Change Score Group 2	Standard Deviation Group 1	Standard Deviation Group 2
State Anxiety	T0 to T1	100	98%	2.71	-2.78	8.24	7.43
State Anxiety	T0 to T1	150	100%	2.71	-2.78	8.24	7.43
State Anxiety	T0 to T1	200	100%	2.71	-2.78	8.24	7.43
State Anxiety	T0 to T1	300	100%	2.71	-2.78	8.24	7.43
State Anxiety	T0 to T1	400	100%	2.71	-2.78	8.24	7.43
State Anxiety	T0 to T1	61	85%	2.71	-2.78	8.24	7.43
IES-Total	T0 to T1	100	100%	0.29	-1.78	1.70	3.19
IES-Total	T0 to T1	150	100%	0.29	-1.78	1.70	3.19
IES-Total	T0 to T1	200	100%	0.29	-1.78	1.70	3.19
IES-Total	T0 to T1	300	100%	0.29	-1.78	1.70	3.19
IES-Total	T0 to T1	400	100%	0.29	-1.78	1.70	3.19
IES-Total	T0 to T1	46	85%	0.29	-1.78	1.70	3.19
Knowledge	T0 to T1	100	97%	1.70	-1.50	6.11	3.02
Knowledge	T0 to T1	150	100%	1.70	-1.50	6.11	3.02
Knowledge	T0 to T1	200	100%	1.70	-1.50	6.11	3.02
Knowledge	T0 to T1	300	100%	1.70	-1.50	6.11	3.02
Knowledge	T0 to T1	400	100%	1.70	-1.50	6.11	3.02
Knowledge	T0 to T1	68	85%	1.70	-1.50	6.11	3.02
State Anxiety	T0 to T2	100	13%	-2.43	5.00	4.04	14.58
State Anxiety	T0 to T2	150	23%	-2.43	5.00	4.04	14.58
State Anxiety	T0 to T2	200	34%	-2.43	5.00	4.04	14.58
State Anxiety	T0 to T2	300	55%	-2.43	5.00	4.04	14.58
State Anxiety	T0 to T2	400	72%	-2.43	5.00	4.04	14.58
State Anxiety	T0 to T2	512	85%	-2.43	5.00	4.04	14.58
IES-Total	T0 to T2	100	79%	-1.00	-2.17	1.53	2.86
IES-Total	T0 to T2	150	95%	-1.00	-2.17	1.53	2.86
IES-Total	T0 to T2	200	99%	-1.00	-2.17	1.53	2.86
IES-Total	T0 to T2	300	100%	-1.00	-2.17	1.53	2.86
IES-Total	T0 to T2	400	100%	-1.00	-2.17	1.53	2.86
IES-Total	T0 to T2	114	85%	-1.00	-2.17	1.53	2.86
Knowledge	T0 to T2	100	48%	5.86	4.40	4.30	3.05
Knowledge	T0 to T2	150	72%	5.86	4.40	4.30	3.05
Knowledge	T0 to T2	200	86%	5.86	4.40	4.30	3.05
Knowledge	T0 to T2	300	98%	5.86	4.40	4.30	3.05
Knowledge	T0 to T2	400	100%	5.86	4.40	4.30	3.05
Knowledge	T0 to T2	194	85%	5.86	4.40	4.30	3.05

Power for Promis Depression and Promis Anxiety

With 200 evaluable patients per arm, there is 91% power to detect an effect size of 0.33 (as fraction of standard deviation), using t-test at two-sided significance level 0.005. Based on data from 92 children/adolescents, Hinds et al. (2012) reported standard deviation of 10.74 for Promis Depression and 12.5 for Promis Anxiety, respectively. Assuming the standard deviations for these two measurements in our proposed study are similar, the following table gives the absolute difference that can be detected with 91% power, under different assumptions for the correlation between the measurements across two timepoints, at two-sided significance level 0.005.

Variable	Correlation	Standard deviation of change	Effect size (as fraction of standard deviation)	Absolute difference	Power
Promis Depression	0.4	11.8	0.33	3.89	91%
Promis Depression	0.6	9.6	0.33	3.17	91%
Promis Depression	0.8	6.8	0.33	2.24	91%
Promis Anxiety	0.4	13.7	0.33	4.5	91%
Promis Anxiety	0.6	11.2	0.33	3.7	91%
Promis Anxiety	0.8	7.9	0.33	2.6	91%

Rev. 7/17

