Patients on both Arms A and B will be asked to complete a total of four surveys electronically (see Section 0). A baseline survey (T0) will be administered immediately following registration to COMET. A second survey (T1) will be administered following the intervention/usual care. An electronic link to the T1 survey will be emailed to all patients at 7 days following completion of the baseline survey (T0). A third survey (T2) will be sent to all patients within three days following their receipt of their tumor profile results. An electronic link to a fourth survey (T3) will be emailed to all patients three months following receipt of tumor profile results.

All patients will receive periodic email reminders to complete surveys.

We will coordinate COMET study activities closely with MATCH or other tumor profile procedures to ensure that surveys do not alter the treatment schedule. If participants have not completed surveys, this will not prevent next steps in their care or other tumor profile activities.

We will test surveys and assess burden and completion rates. If there is evidence of burden, we will revisit length and prioritize outcomes and constructs of interest.

Rev. 2/17

5.2.2 Secondary Genetic Counseling Substudy (Step 2 – Arm D and Arm E):

As shown in the study schema, all participants who meet inclusion criteria and criteria for a potential germline mutation identified with molecular tumor profiling at a participating substudy site will be offered the study (up to accrual of 100 patients).

- Genetic Counseling:

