Changes in knowledge and distress (state anxiety, general anxiety, general depression and cancer specific distress) from baseline to post-pre-test genetic counseling (T0SS to T1SS) and baseline to post-test for those who proceed with confirmatory genetic testing (T0SS to T2SS) will be described using descriptive statistics (e.g. means, standard deviations, proportions, 95% confidence intervals). Multiple linear regressions will be fit to further investigate temporal changes. Again, regression parameters will be estimated using GEE to account for correlated data over time. Unstructured working correlation matrices for GEE will be considered first unless there are model convergence problems, in which case exchangeable working correlation matrices will be used instead. In the regressions, survey wave as dummy indicator (0/1 variables) will be included as covariates. As there are three survey time points, we include two dummy indicators for T1 and T2 (leaving T0 as the baseline reference time period). We will also include potential baseline confounding variables in the models (e.g. age, sociodemographic variables).

Other exploratory endpoints include communication to others, satisfaction and regret/disappointment related to genetic counseling service or germline genetic test results. Summary statistics will be provided.

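### Step 2 change scores use two baseline definitions: Arm D's knowledge and distress baseline is carried over from the Step 1 T2 survey with no age limit, while Arm E's is answered at Step 2 entry

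*Combined protocol and SAP*

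**What the plan says.** **Arm D (from Step 1 Arms A or B).** Section 6.2, footnote C, and section 5.2.2 fill T0SS from the Step 1 T2 survey: "information taken from T2 (see Sec. 6.1) will be used to pre-populate T0SS, and only the remaining items in T0SS" have to be answered. Footnote C exempts two instruments, Uncertainty and Perceived Utility: these "assessments in T2 are exceptions, and must be completed in T0SS for all patients".

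**Arm E (from Arm C).** Here "the entire T0SS will be completed as the baseline survey".

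**Timing of T2.** Section 5.2.1: "A third survey (T2) will be sent to all patients within three days following their receipt of their tumor profile results". Under section 5.4, surveys stay open until they are completed or the patient goes off study, and completion dates are recorded.

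**Use of T0SS.** Section 7.2.2 describes changes in knowledge, state anxiety, general anxiety, general depression and cancer specific distress "from baseline to post-pre-test genetic counseling (T0SS to T1SS") and from T0SS to T2SS. It then fits a GEE regression with survey-wave indicators and baseline confounders, for which age and sociodemographic variables are the examples. Section 7.2 covers Arms D and E together. Section 5.1.2 makes the substudy single-arm, and section 7.2.1 calls it exploratory, with uptake of counseling and of germline testing as primary endpoints.

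**The concern.** A change score is a contrast between two dates, so its meaning depends on when the first measurement was taken. In Arm E the first date is Step 2 entry. In Arm D, for the carried-over instruments, it is whenever T2 was answered, normally soon after the tumor report. Between that point and Step 2 entry come screening against the gene criteria (with extra vetting for some genes, section 3.2.2.1), notification and consent (section 5.3), and the faxed report and call (section 4.2.3.3). The plan does not limit how long this takes.

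State anxiety is the instrument least suited to carrying over, on the plan's own description in section 5.5.5: "The state scale is a sensitive indicator of transient or situational changes in anxiety".

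At stake are secondary objective 2.2.2(b), the cognitive and affective responses to confirmatory germline testing, and the part of hypothesis 4 (section 1.2) that links counseling to changes in knowledge and distress. With no control group, the before/after change is the only evidence on either. Pooling two baseline definitions makes that change harder to interpret.

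**Working it through.** The plan gives no sample size, power or precision for the Step 2 change scores, so there is no figure to reproduce. The check compares the text and then illustrates scale.

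**1. Which instruments are carried over.** From the assessment tables in 6.1 and 6.2 and the item counts in 5.5:

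| Instrument at T0SS | Also in T2? | Arm D baseline | Items |
|---|---|---|---|
| Knowledge of Genetic Disease | yes | copied | 3 + 7 + 3 + 1 = 14 |
| PROMIS anxiety and depression | yes | copied | 4 + 4 = 8 |
| State anxiety | yes | copied | 20 |
| Cancer specific distress | yes | copied | 7 + 7 = 14 |
| Uncertainty; Perceived Utility | yes, for tumor testing | asked afresh | – |
| Knowledge of inherited disease | no | asked afresh | – |

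Copied items: 14 + 8 + 20 + 14 = 56. They cover all four distress measures in 7.2.2 and the general knowledge scale.

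**2. What bounds the gap.** No section sets a maximum age for T2 answers or requires T2 to precede GC Visit 1. Section 5.7 expects both steps together to last no more than 5 months. A tested patient has a T3SS survey 3 months after germline results, so on that expectation the gap is below 5 − 3 = 2 months. An untested patient has no such survey, and the expectation constrains the gap much less. Neither is an enforced limit.

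**3. How drift enters.** For a carried-over instrument in Arm D:

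T1SS − T2 = (T1SS − value at entry) + (value at entry − T2).

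The last bracket is the drift d. In Arm E it is absent. If a share p of the patients analysed has a copied baseline, the pooled mean change shifts by p × d. Section 7.2.2 names no term for arm, baseline source or T2 age that would absorb it.

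**4. Illustration for state anxiety.** Assumptions: all 100 patients contribute; SD of change 8.24 (Step 1 power table, T0 to T1, group 1); p and d are assumed, because the documents give neither.

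- 95% half-width = 1.96 × 8.24 / √100 = 1.62 points. With the smallest and largest state-anxiety SDs in that table (4.04 and 14.58) it is 0.79 and 2.86.
- Standard error s = 8.24 / 10 = 0.824. With b = p × d, coverage of the true change after entry is Φ(1.96 − b/s) − Φ(−1.96 − b/s).

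| p | d = 2: shift (coverage) | d = 5: shift (coverage) |
|---|---|---|
| 25% | 0.5 (91%) | 1.25 (67%) |
| 50% | 1.0 (77%) | 2.5 (14%) |
| 75% | 1.5 (56%) | 3.75 (0.5%) |

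If d is near zero, as when Step 2 starts within days of T2, the shift is near zero for any p.

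**The case against.** The strongest reply is that this is an exploratory pilot whose primary endpoints, uptake of counseling and of testing, do not depend on T0SS. Pre-filling spares patients with advanced cancer up to 56 repeated items. Completion dates are recorded, and section 5.4 lets the study team use them to decide which data enter an analysis. Nothing in 7.2.2 forbids reporting by arm, and its confounder list is open. All of this stands and limits the weight of the point. It does not remove the inconsistency: the plan leaves the handling to be decided later and states no rule.

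A reader might also infer three stronger things that the documents do not support:

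- **That settling or rising distress is credited to counseling in Arm D but not in Arm E.** Arm E also enters after tumor results and has no control, so its own course after entry falls inside its change score. The arms differ only in the drift between T2 and Step 2 entry.
- **That the power table shows the drift to be several points.** Its state-anxiety changes of −2.43 and 5.00 run from T0 to T2, across disclosure, with opposite signs. Section 1.5.1 reports only 14 pilot patients with post-disclosure surveys. No figure describes change after T2.
- **That about half of Arm D would have no baseline.** Section 7.1.1 says "With the completion rate for both T0 and T2 surveys at approximately 45" percent, which is joint completion. Section 4.3 bars randomized patients without T0 from Step 2. T0 completion is at least the 60% T0-and-T1 rate, so T2 completion given T0 is between 45/100 = 45% and 45/60 = 75%, leaving 25% to 55% without T2 if Step 2 joiners respond like the rest. Those patients would most naturally answer the whole T0SS, which gives them a baseline at entry and shrinks the problem.

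**Conclusion.** The point holds as a baseline inconsistency of unknown size. Arm D's general knowledge and distress changes start at T2, Arm E's start at Step 2 entry, and 7.2.2 neither separates nor adjusts for the two. With 2 points of drift the pooled state-anxiety mean would move by 0.5 to 1.5 points, against a half-width of about 1.6. That rests on the assumed drift, an assumed Arm D share of 25% to 75%, and an SD borrowed from the Step 1 pilot.

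Uptake, Uncertainty, Perceived Utility and inherited-disease knowledge are not affected. It would be too strong to conclude that objective 2.2.2(b) goes unanswered, or that a fresh baseline would isolate the effect of counseling. A fresh baseline would align the arms and remove the drift before entry, but an uncontrolled pilot cannot separate counseling from time.

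**What to change.** - **Section 7.2.2:** report the change scores separately for Arms D and E, or add a baseline-source term to the GEE. Report the distribution of the T2-to-T0SS gap from the completion dates already held. This also serves patients already enrolled.
- **Section 6.2, footnote C, and section 5.2.2:** allow copying only when T2 was completed before GC Visit 1 and within a short, prespecified window before T0SS. Otherwise, including when there is no T2, the patient answers these items at T0SS. The documents offer no basis for a particular window, so the study team should choose and justify it.

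The reporting change costs almost nothing beyond smaller groups in the by-arm summaries. The copying rule needs a wording change and a date check in the survey system, plus up to 56 items, once, for Arm D patients whose T2 falls outside the window.
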